12.6.3 Efficacy Analyses

The secondary endpoints are the change in frequency and severity of vasomotor symptoms and hot flash severity score at Week 1 and Week 2 relative to Baseline.

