²Key inclusion/exclusion criteria must be re-assessed before conducting any other baseline assessments. All baseline assessments to be conducted on Day -1 (and/or Day 1 as indicated) to be conducted prior to dosing unless otherwise indicated (See [Section 7](#)).

³Subjects will be required to fast for approximately 8 hours prior to their Screening Visit and Day 16. Subjects will be required to fast for 12 hours prior collection of laboratory sample for CTX on Day 1 and Day 14. CTX blood sample must be collected prior to dosing. Subjects will be required to fast for 4 hours post morning dose on Day 1 and Day 14. Subjects will also be required to fast for 8 hours prior to Day -1 and from midnight prior to dosing (approximately 8 hours) Day 2 and Day 7. Water will be allowed *ad libitum*.

⁴Vital signs, including oral body temperature, pulse oximetry, respiratory rate, and sitting and standing BP and heart rate, will be performed daily during the study period approximately 60 minutes prior to am dosing. The minimal positional time for collection of the orthostatic vital signs is approximately 5 minutes sitting and approximately 2 minutes standing prior to collection of vital signs.

⁵Randomization can occur on Day -1 or Day 1 but must occur before dosing.

⁶Continuous hot flash diary: Instructions on the use of the continuous hot flash diary will be provided at Screening. Subjects are required to record the frequency and severity of the hot flash (scale 1 to 3) in a continuous hot flash diary for 2 weeks prior to randomization (during the day and at night). Subjects will record the frequency and severity of hot flash while in the clinic Day -1 to Day 16 (during the day and the night). Subjects are also to record the time they went to sleep, and morning wake up time.

⁷Luteinizing hormone (LH) sampling on Day-1 and predose and every 60 mins starting at 60 minutes after dose 0 to 8 hrs Day 1, Day 2, and Day 14.

⁸Study drug will be administered twice daily, approximately 12 hours apart (morning and evening dose) from Day 1 through Day 14. All applicable study procedures must be completed prior to administration of the morning study drug. Subjects will be required to fast for 12 hours prior to study drug administration and for 4 hours post morning dose on Days 1 and 14. Subjects will be required to fast for 8 hours prior to morning study drug administration on Days 2 and 7. No fasting is required on Days 3 – 6 or Days 8 – 13.

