⁹PK Sampling at predose, 0.5, 1.0, 1.5, 2.0, 2.5, 3.0, 4.0, 5.0, 6.0, 8.0, 12.0 (prior to evening dose) and 15.0 hours post morning dose on Day 1 and Day 14, as well as predose (morning) on Day 2 and Day 7. Plasma samples will also be collected 24 hours (Day 15) and 48 hours (Day 16) after the morning dose on Day 14.

¹⁰Predose samples for PK and LH to be taken within 30 minutes prior to dose administration.

¹¹Where possible, all subjects who are withdrawn or withdrawn from the study early will undergo the Early Termination Visit assessments.

¹²14-Day Safety Follow-up Visit; subjects will be contacted by telephone 14 days (± 4 days) following the final dose of study drug on Day 14, unless deemed by the investigator that a clinic visit is more appropriate to follow up an adverse event.

¹³If the Screening Period is >28 days the following procedures must be repeated such that the most recent evaluation occurs within 28 days of their scheduled randomization: biochemistry, hematology, coagulation, vital signs, 12-lead ECG, physical examination. If the subject has completed (or partially completed) the continuous Hot Flash Diary this must still be repeated, and a new continuous hot flash diary started on the new planned Day -15 and completed for the 2 weeks up to Day -2. Eligibility will be assessed on the repeated continuous hot flash diary, not the initial one. If the subject had not started completing their screening continuous hot flash diary at the time screening was put on hold, they will start this screening continuous hot flash diary on the re-scheduled Day -15.

¹⁴To be collected predose on dosing days.

¹⁵Time and duration of Mortara Surveyor ECG collection must be identical on Day -1, Day 1, and Day 14 and must be planned in relation to predose and 15 hrs postdose PK time points.

¹⁶The safety ECG readings will be performed approximately 1 hour after the scheduled morning dose on dosing days.

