5 SELECTION AND WITHDRAWAL OF SUBJECTS

5.1 Inclusion Criteria

To be eligible to participate in this study, subjects must meet all the following criteria:

1. Post-menopausal female subjects 40-65 years of age, inclusive.
Menopause will be defined as:
 - a. At least 12 months of spontaneous, continuous amenorrhea, or
 - b. At least 6 months of spontaneous, continuous amenorrhea with serum FSH levels > 40 mIU/mL at screening, or
 - c. At least 6 weeks postsurgical bilateral oophorectomy with or without hysterectomy.
2. At baseline women:
 - a. With an average of ≥ 7 and ≤ 20 moderate to severe hot flashes/day for 2 weeks prior to randomization (per continuous hot flash diary) ([Sloan, 2012](#)). The minimum number of hot flashes on each day during the 2 weeks prior to randomization must be at least 7.
 - b. That have a change of $< 50\%$ in average 24-hour hot flash frequency 2 weeks prior to randomization.
 - Moderate: defined as sensation of heat with sweating, able to continue activity.
 - Severe: defined as sensation of heat with sweating, causing cessation of activity.
3. Able to understand and comply with the requirements of the study and sign Informed Consent forms.
4. Have not participated in any clinical research study evaluating another investigational drug, device or therapy within 30 days or within 5 half-lives (whichever is longer), of the investigational drug prior to consenting to study entry.

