10 EFFICACY ASSESSMENTS

Subjects will record VMS, including NTA, in a continuous hot flash diary during the Screening Period (2 weeks prior to Day -1) to assess eligibility. During confinement subjects will record VMS using a continuous hot flash diary. A description of the methods for VMS assessments is described in Sections 10.1 and 10.2.

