12.4 Secondary Endpoints

The secondary endpoints are:

- Change in frequency of vasomotor symptoms at Week 1 and Week 2 relative to Baseline
- Change in severity of vasomotor symptoms at Week 1 and Week 2 relative to Baseline
- Change in hot flash severity score at Week 1 and Week 2 relative to Baseline

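### Does the undefined diary Baseline leave the hot flash endpoints open to a choice that matters?

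*Combined protocol and SAP*

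**What the plan says.** Section 12.4 lists three diary endpoints, the first being "Change in frequency of vasomotor symptoms at Week 1 and Week 2 relative to Baseline"; severity and the severity score follow the same form. Section 12.6.3 repeats the list, ending with the "hot flash severity score at Week 1 and Week 2 relative to Baseline", and names no model, no baseline days and no days for either week.

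The passages that bear on Baseline are these:

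- Inclusion criterion 2 (Section 5.1) opens with "At baseline women" and then sets its count rules over the 2 weeks before randomization, including: "The minimum number of hot flashes on each day during the 2 weeks prior to randomization must be at least 7".
- Table 1 footnote 6 has subjects record hot flashes "in a continuous hot flash diary for 2 weeks prior to randomization".
- Section 10 has them recorded "in a continuous hot flash diary during the Screening Period (2 weeks prior to Day -1) to assess eligibility".
- Table 1 footnote 13 says that a repeated diary is "started on the new planned Day -15 and completed for the 2 weeks up to Day -2".
- Table 1 footnote 2, attached to the Day -1 and Day 1 columns, reads: "All baseline assessments to be conducted on Day -1 (and/or Day 1 as indicated) to be conducted prior to dosing unless otherwise indicated".

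Footnote 5 lets randomization fall on Day -1 or Day 1. Dosing ends on the evening of Day 14, and the diary runs to Day 16. Section 12 says that an SAP with the specific analyses will be approved before database lock and unblinding. The text of that SAP is not in the supplied document.

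**The concern.** A change score needs a stated starting point, and here two can be argued for. The 2-week diary averages 14 days but is kept before admission. Day -1 is a single day, but it is the only pre-dose day recorded in the clinic, where all follow-up is recorded. Section 10 describes the earlier diary as an eligibility tool, and footnote 2 speaks of baseline on Day -1, so a reader could settle on Day -1.

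One diary day is much noisier than a 14-day mean. With 10 to 14 subjects per arm, that noise would pass straight into an unadjusted change score. A baseline chosen after unblinding would also be an avoidable freedom in comparisons tested at 0.05 without multiplicity adjustment. If the window really mattered more than the choice of model, it would be the first thing to fix.

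**Working it through.** **1. The plan's own figures.** The stated sample size is consistent: 4 x 10 = 40 and 4 x 14 = 56. Section 12.1 gives no SD, effect or power, so there is no stated precision to reproduce. Every SD below is an assumption.

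**2. The passages side by side.**

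| Place | Days | Role of the text |
|---|---|---|
| Criterion 2 | 2 weeks before randomization | calls this baseline and applies it to counts |
| Footnote 6 | 2 weeks before randomization, then Day -1 to Day 16 | recording instruction |
| Section 10 | 2 weeks before Day -1 | eligibility |
| Footnote 13 | Day -15 to Day -2 | repeated diary only |
| Footnote 2 | Day -1 and/or Day 1 | assessments precede dosing; diary not named |
| Section 10.1 | in clinic from Day -1 | recording instruction |
| Synopsis, Section 4.1 | on-study diary from Day 1 | recording instruction |

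Only criterion 2 joins baseline, hot flash counts and a period.

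**3. How far the 2-week wordings differ.** Day -15 to Day -2 is 15 - 2 + 1 = 14 days. That is the same window as 2 weeks before Day -1, and as 2 weeks before randomization when randomization is on Day -1. If randomization is on Day 1, the window becomes Day -14 to Day -1, and 13 of the 14 days are shared. Swapping one day moves the mean by the difference of two daily counts divided by 14. With an assumed daily variance of 10 and independent days, the SD of that shift is sqrt(2 x 10)/14 = 0.32 flashes/day.

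**4. Cost of Day -1.** Let B be the between-subject SD, D the daily variance, R the SD of individual response, s the slope of follow-up on true baseline, and k the number of baseline days. Follow-up is a 7-day mean. Without autocorrelation:

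- VX = B² + D/k; VY = s²B² + R² + D/7; C = sB²
- change-score variance = VX + VY - 2C
- ANCOVA residual variance = VY - C²/VX

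Take B = 3, D = 10, R = 3. Then VX = 9 + 10/14 = 9.71 for 14 days, and 9 + 10 = 19 for Day -1.

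For s = 1, VY = 9 + 9 + 1.43 = 19.43 and C = 9:

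- change, 14 days: 9.71 + 19.43 - 18 = 11.14, SD 3.34
- change, Day -1: 19 + 19.43 - 18 = 20.43, SD 4.52
- ANCOVA, 14 days: 19.43 - 81/9.71 = 11.09, SD 3.33
- ANCOVA, Day -1: 19.43 - 81/19 = 15.17, SD 3.89

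For s = 0.5, VY = 2.25 + 9 + 1.43 = 12.68 and C = 4.5. The same four SDs are 3.66, 4.76, 3.25 and 3.41.

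Ratios of SDs:

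| s | Day -1 / 14-day, change | Day -1 / 14-day, ANCOVA | change / ANCOVA, 14-day | change / ANCOVA, Day -1 |
|---|---|---|---|---|
| 1 | 1.35 | 1.17 | 1.00 | 1.16 |
| 0.5 | 1.30 | 1.05 | 1.12 | 1.40 |

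At s = 1 and 12 per arm, the 95% CI half-width (2.074 x SD x sqrt(2/12)) is 2.8 v 3.8 flashes/day for change and 2.8 v 3.3 for ANCOVA (14-day v Day -1). Power for an assumed difference of 4/day is 0.84 v 0.58 and 0.84 v 0.71.

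A grid of 243 cases was run: B 2, 3, 4; D 4, 10, 15; R 1.5, 3, 4.5; s 1, 0.75, 0.5; autocorrelation 0, 0.3, 0.6. The window ratio runs from 1.05 to 1.88 for change and from 1.01 to 1.50 for ANCOVA. Averaged over both settings, the window outweighs the model in 53% of cases: 96% at s = 1, 63% at 0.75 and none at 0.5. It does so in both paired comparisons in only 16%.

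**5. With the trial's eligibility rule applied.** In a separate simulation, daily counts were Poisson, true rates lognormal (median 10, log-SD 0.35), and the dose arm had 30% fewer flashes than placebo. Power (%) at n = 10 per arm:

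| Placebo factor / log-SD of response | Change, 14-day | Change, Day -1 | ANCOVA, 14-day | ANCOVA, Day -1 |
|---|---|---|---|---|
| 0.6 / 0.2 | 66 | 25 | 79 | 68 |
| 0.6 / 0.4 | 32 | 18 | 34 | 31 |
| 0.8 / 0.2 | 78 | 37 | 82 | 71 |
| 0.8 / 0.4 | 33 | 22 | 33 | 31 |

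Moving to Day -1 costs 41, 14, 41 and 11 points with a change score, but 11, 3, 11 and 2 with ANCOVA. On Day -1, moving from change to ANCOVA gains 43, 13, 34 and 9 points. In the first row, ANCOVA on Day -1 (68) even passes the change score on 14 days (66).

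**6. Effect on the estimate.** Both windows precede dosing, so randomization balances them in expectation. In a further set of simulations, with proportional response, the mean dose-placebo differences under the two windows agreed to within 0.05 flashes/day (for example -4.16 v -4.13).

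**The case for a change.** The best case for a change is that no passage states the definition, that both readings have text behind them, and that settling it costs a few sentences. Table 1 marks the diary on Day -1, and Section 10.1 has subjects recording in the clinic from that day, so a Day -1 value exists. Day -1 also costs precision in every one of the 243 cases. The mITT population requires a baseline efficacy measurement, so the definition might decide who is analysed.

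Part of this stands. The definition is missing, and a Day -1 baseline would be a poor choice for an unadjusted change score. Subjects also move from home to clinic between the 2-week diary and follow-up, so within-arm changes mix that move with drug effect. The dose-minus-placebo difference removes it.

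The rest is weaker. Footnote 2 does not name the diary, which has its own footnote. Day -1 is the admission day with no stated time, so it may be only partly spent in the clinic. Under the 2-week reading, mITT membership is hardly at issue, because criterion 2 already demands counts on every day of those 2 weeks. Late choice of window is what approval of the SAP before unblinding is there to prevent.

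**Conclusion.** The concern does not call for a change. The protocol omits a detail that belongs in the SAP, and Section 12 already requires that SAP before database lock and unblinding. From the text as it stands, analysts would take the 2-week mean as Baseline. Fourteen dosing days divide into Days 1-7 and 8-14, which leaves Days 15 and 16 as off-drug days. The differing descriptions of the 2-week window disagree by at most one day in 14.

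The claim that the window outweighs the model does not hold in general. It tends to hold when follow-up tracks baseline one for one, and it reverses at a slope of 0.5. The largest losses, such as 66% to 25% power, need a single-day baseline and an unadjusted change score together. No passage plans either; ANCOVA appears only in the abbreviation list. On the 14-day baseline, the variance ratio of change to ANCOVA at n = 10 ran from 0.97 to 1.29 over all assumed variants, so adjustment gives anything from a 3% loss to a moderate gain.

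All these sizes rest on assumed counts and variances. What is at stake is the precision of secondary, preliminary comparisons, not bias in the treatment difference. The primary PK and safety objectives are untouched.

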12.6.4 Exploratory Analyses

The exploratory analyses will include summary statistics.

12.7 Changes in the Conduct of the Study or Planned Analyses

Only Acer or its designee may modify the protocol. Any change in study conduct requested by the investigator will be made only after consultation with Acer or its designee, who will then issue a formal protocol amendment to implement the change. The only exception may occur when the investigator considers that a subject's safety is compromised without immediate action. In these circumstances, immediate approval of the chairman of the IRB must be sought, and the investigator should inform Acer or its designee and the full IRB within 2 working days after the emergency occurs. With the exception of minor administrative or typographical changes, the IRB must review and approve all amendments. Amendments that have an impact on subject risk or the study objectives, or require revision of the ICF, must receive approval from the IRB prior to their implementation.

When a protocol amendment substantially alters the study design or the potential risks or burden to subjects, the ICF will be amended and approved by the IRB, and all active subjects will again provide written informed consent.

13 ADMINISTRATIVE CONSIDERATIONS

13.1 Compensation, Insurance, and Indemnity

There will be no charge to subjects to be in this study. Acer will pay all costs of tests, procedures, and treatments that are part of the study. In addition, Acer may defer the cost of travel if the company determines that the costs will impose a hardship on subjects. Acer will not pay for any hospitalizations, tests, or treatments for medical problems of any sort, whether or not related to the study subject's disease that is not part of this study. Costs associated with hospitalizations, tests, and treatments should be billed and collected in the way that such costs are usually billed and collected.

The investigator should contact Acer or its designee immediately upon notification that a subject has been injured by the study drug or by procedures performed as part of the study. Any subject who experiences a study-related injury should be instructed by the investigator to seek medical treatment at a prespecified institution.

The treating physician should bill the subject's health insurance company or other third-party payer for the cost of this medical treatment. If the subject has followed the investigator's instructions, Acer will pay for reasonable and necessary medical services to treat the injuries caused by the study drug or study procedures if these costs are not covered by health insurance or another third party that usually pays these costs. In some jurisdictions, Acer is obligated by law to pay for study-related injuries without prior recourse to third party payer billing. If this is the case, Acer will comply with the law.

13.2 Ethical Considerations

The final study protocol, including the final version of the ICF and/or other subject information, must be approved or given a favorable opinion in writing by an IRB. The investigator must submit written IRB approval to Acer before they can enroll any subject into the study. The investigator is responsible for providing the IB and any other available safety information and information about payments and compensation available to subjects to the IRB for review.

The investigator is responsible for informing the IRB of any amendment to the protocol in accordance with local requirements. A favorable opinion on amendments will be obtained prior to implementation, unless the amendment is necessary to reduce immediate risk to study participants. In addition, the IRB must approve all advertising used to recruit subjects for the study. The protocol must be reapproved by the IRB/upon receipt of amendments and annually, as local regulations require.

The investigator is also responsible for providing the IRB with reports of any reportable serious adverse drug reactions from any other study conducted with the investigational product, according to local regulations and guidelines. Acer will provide this information to the investigator.

The clinical trial will not be initiated, and study drug supplies will not be shipped to the clinical unit, until appropriate documents from the IRB, confirming unconditional approval of the protocol, ICF, and all recruiting materials, are obtained by the investigator and copies are received by Acer or its designee. The approval must refer to the study by protocol title and number, identify the documents reviewed, and include the date of review. The investigator will

provide appropriate reports on the progress of the study to Acer or its designee and to the IRB in accordance with applicable governmental regulations and in agreement with policy established by Acer or its designee.

Progress reports and notifications of SAEs will be provided to the IRB according to local regulations and guidelines. Investigators or Acer or its designee will provide reports to the IRB as requested, at a minimum annually, and after the study is complete.

13.2.1 Basic Principles

This research will be carried out in accordance with CFR, Good Clinical Practice (GCP), 21 CFR Parts 50 and 312, the principles enunciated in the Declaration of Helsinki, and the International Council for Harmonisation (ICH) harmonized tripartite guideline regarding GCP.

13.2.2 Institutional Review Board

This protocol will be reviewed by an IRB and the study will not start until the IRB has approved the protocol or a modification thereof. The IRB is constituted and operates in accordance with the principles and requirements described in the US CFR (21 CFR Part 56). The board must be ICH compliant.

13.2.3 Informed Consent

A properly written and executed ICF in compliance with the Declaration of Helsinki, ICH GCP, and the appropriate US and local regulations will be obtained from each subject prior to enrolling the subject in the study. A copy of the approved ICF and, if applicable, a copy of the approved subject information sheet, must be received by Acer or its designee prior to delivery of study drug and prior to conducting any study procedures.

The purpose of the study, the procedures to be carried out, and the potential hazards will be described to the subjects in non-technical terms. The subject should be given the opportunity to ask questions and allowed time to consider the information provided. Subjects will be required to read, sign, and date an ICF summarizing the discussion prior to screening and will be assured that they may withdraw from the study at any time without jeopardizing their medical care. Subjects will be given a copy of their ICF.

13.2.4 Subject Confidentiality and Data Protection

Participant confidentiality is strictly held in trust by the participating investigators, their staff, and Acer and their agents. This confidentiality is extended to cover testing of biological samples in addition to the clinical information relating to participants. Therefore, the study protocol, documentation, data, and all other information generated will be held in strict confidence. No information concerning the study, or the data will be released to any unauthorized third party without prior written approval of Acer.

The study monitor (e.g., CRA, medical monitor), other authorized representatives of Acer, representatives of the IRB, or regulatory inspectors may inspect all documents and records required to be maintained by the investigator, including but not limited to, medical records (office, clinic, or hospital) and pharmacy records for the participants in this study. The clinical

study site will permit access to such records. An agreement for disclosure of any such information will be obtained in writing and is included in the statement of informed consent.

The study participant's contact information will be securely stored at each clinical site for internal use during the study. At the end of the study, all records will continue to be kept secured against unauthorized access for as long a period as dictated by local IRB and institutional regulations.

The investigator will maintain a list of subject's names and identifying information (e.g., subject's hospital number, unique subject number). This list will not be collected by Acer but may be viewed or audited by Acer or regulatory authorities.

The ICF will explain that study data will be securely stored in a computer database, maintaining confidentiality in accordance with national data protection legislation. All data computer processed by Acer or designee will be identified by unique subject number/randomization code/site number only.

When personal data on subjects are stored or processed by computer, the data must be secured, and password protected to prevent disclosure to unauthorized third parties. The pertinent sections of the data protection laws in the country in which the protocol is being conducted will be complied with in full.

The ICF will explain that, for data verification purposes, authorized representatives of Acer, regulatory authorities, or IRB may require direct access to parts of the hospital or study center records relevant to the study, including subject's medical history.

